For those randomized to the CtC intervention group, the CtC letter, electronically signed on behalf of [name] of NNHSC, will be created by the EHR system on NNHSC letterhead and mailed by the care coordinator or research assistant. One day after CtC letter mailing, the first CtC text message will be sent to notify CtC participants of the coming letter. The remaining 4 text messages will be sent per the timeline described above. After a 12-day participant opt-out period (described in the letter), names and contact details, including best times to be called, will be sent by the EHR referral system to the Quitline at 7:00pm each day a referral is made. Participants will be called within two days of referral. NNHSC and each of its clinics will have a unique code that will be sent via the EHR system to the Quitline along with an encrypted referral file of Choose to Change participants. A different code, but unique to NNHSC, will be used to identify and track outcomes for Usual Care participants. All codes will be specific to this study. They will serve to identify the study protocol: cessation-focused counseling and NRT or reduction-refocused counseling and NRT as a first step to smoking cessation. Once reached by the Quitline, the participant's referral data will be shown on one screen and the study protocol via the virtual library will be shown on a second screen. The protocol description and required data fields will ensure that participants are provided reduction-focused counseling if chosen, free NRT if willing and deemed safe, and that additional project-required data are collected. Patient-specific outcomes will be transmitted to NNHSC at the end of each day.

Proactive Quitline Treatment for Choose to Change and Usual Care Conditions

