Participants in both treatment conditions will have the opportunity to receive the same proactive Quitline treatment consisting of person-centered behavior counseling and NRT. The Quitline protocol relies on treatment determined to be effective in the 2008 U.S. PHS Clinical Practice Guideline.⁵ Participants who are reached and who accept treatment will first be asked for basic sociodemographic and smoking information. After registration and brief assessment, either smoking cessation- or reduction- focused treatment will be delivered depending on patient preference. Participants who choose reduction as their initial treatment goal will be guided toward setting a quit date aided by NRT. For all participants who engage in treatment, a self-help packet (Quit-Kit) will be mailed to provide written information on the topics covered during the initial phone session. Most calls last about 30 minutes, with the behavior counseling portion lasting about 15 minutes. A free 8-week course of NRT (patch, gum, or lozenge) will be mailed in two week allotments to participants who are willing to set a quit date and interested in and eligible to use NRT (i.e., free of medical contraindication). Per Quitline policy for Chicago residents, NRT is offered at no cost for uninsured residents and reduced cost for those who have Medicaid insurance. Because free NRT increases use of quitline treatment,^{46,104} NRT will be made available at no cost to all participants to eliminate differential cost by insurance type as a potential confounder of intervention effects.

If a participant is reached by the Quitline counselor but has not received the Choose to Change letter, smoking cessation or reduction treatment will be offered and delivered according to the participant's preference. For participants not reached during the first call attempt, the Quitline counselor will make two more calls in the following two days. A voice message will only be left if the voicemail inbox belongs to the referred participant. If three calls are made without a response, the outreach process will end. The Quitline counselor will either call at times designated by the participant to be convenient or at varying times during the day. The Quitline provides services seven days per week, from 7:00 AM through 11:00 PM.

MEASURES

EHR Characterization of Population

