The EHR query to identify participants will also generate information on the following characteristics: sociodemographic (age, gender, race, ethnicity, marital status, household income, education), smoking history (number of years smoking, past year quit attempts, use of multiple tobacco products, past referral for smoking cessation treatment, including quitline), and healthcare (e.g., date of last clinic visit, type of health insurance, most recent problem list). A second query will be run at the 8-month time point to generate number, dates, purpose of any clinic visit(s) during the study period, whether or not smoking was addressed (a required field in the EHR system), and an updated problem list.

Characterization of Population that Engages in Quitline Treatment

Participants who accept the Quitline call will complete a registration process that includes brief assessment of smoking and smoking history to guide treatment. Information will be obtained on current smoking, including frequency and preference for menthol cigarettes. If non-daily smoking is endorsed, counselors will ask about a typical smoking day. If daily smoking is endorsed, cigarettes per day and time to first cigarette will be obtained. Counselors also ask about how long the participant has been a smoker, number of past quit attempts and, if any, by what method.

Telephone Surveys on Health Behaviors

Because many outcome, moderator, mediator, and control variables cannot be received from the Quitline via the EHR system for participants who do not engage in Quitline treatment, enrolled participants will complete the “NNHSC Health Habits and Wellness service needs survey” of smoking status and moderator, mediator, and control variables via telephone interview at baseline (week -4; 4 weeks before randomization to treatment and letter mailing), 6, 14, and 28 weeks.

Treatment Outcomes

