Treatment engagement will be measured at 6, 14, and 28 (as applicable) weeks after letter mailing, and operationalized as the proportion of participants who accept the proactive Quitline call and accept treatment as defined by completing the counseling session. Participants who return a Quitline call and accept treatment also will be counted as having engaged in treatment. Further, we will assess: 1) the proportion of smokers who request cessation versus reduction counseling; and 2) the proportion of smokers who engage in treatment and who request NRT and (or) schedule a follow-up (proactive or reactive) counseling call.

Treatment utilization will be measured at 6, 14, and 28 (as applicable) weeks and will be defined as the proportion of participants who complete ≥ 1 additional counseling calls and receive and use NRT. The frequency and duration of sessions will also be measured.

Smoking cessation at 6 and 14 weeks will be defined as self-reported abstinence (not even a puff of a cigarette) for ≥ 7 days. At 28 weeks, breath CO will be used to verify abstinence for participants in the original study timeline. For participants in the alternative shorter study timeline, breath CO will be measured at 14 weeks to verify abstinence. Participants will be classified as abstinent if they report not smoking (not even a puff of a cigarette) for ≥ 7 days and have a CO ≤ 8 parts per million (ppm). Participants will be assumed to be smoking if they report smoking, cannot be reached to provide data, fail to provide a breath sample, or provide a breath sample that is >8 ppm.¹⁰⁵ Participants who report abstinence at 28 weeks (original timeline) or 14 weeks (alternative shorter timeline) will be invited for an in-person visit for breath carbon monoxide (CO) measurement to bio-verify abstinence status.

Moderators, Mediators, and Covariates

Hypothesized moderators of Choose to Change effects will be measured at baseline and include readiness to quit smoking,^{96,97} recent smoking reduction,⁵¹ cigarettes per day, time since last clinic visit during which smoking was addressed, initial choice of cessation versus reduction, race/ethnicity, perceived stress, , and discrimination. Hypothesized mediators of intervention effects on treatment engagement, utilization, and cessation will be measured at each survey time point and will include perceived autonomy support, autonomous motivation, confidence in ability to quit, and attitude towards NRT.

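### Exploratory Aim 2: mediation of engagement by week 6 cannot be tested with mediators first re-measured at week 6, after the Quitline call

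*Combined protocol and SAP*

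**What the plan says.** Exploratory Aim 2 (Purpose of Study & Objectives) names engagement, utilization and cessation as outcomes whose intervention effects are to be mediated. The Moderators, Mediators, and Covariates section repeats this and says the mediators "will be measured at each survey time point and will include perceived autonomy support, autonomous motivation, confidence in ability to quit", together with attitude towards NRT. The Telephone Surveys section gives the schedule: "via telephone interview at baseline (week -4; 4 weeks before randomization to treatment and letter mailing), 6, 14, and 28 weeks". The Exploratory Aim 2 paragraph under Data Analysis uses increases from baseline as the mediating quantity, in a structural equation model with bootstrapped paths. Primary Aim 1 defines engagement as a counseling call completed by 6 weeks.

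Call timing comes from three sections:
- **Clinic Workflow:** a 12-day opt-out period, then a Quitline call within two days of referral.
- **Proactive Quitline Treatment:** two more attempts in the next two days, and "If three calls are made without a response, the outreach process will end".
- **Choose to Change Intervention:** the fifth text goes out 8 to 10 days after the first outreach call.

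On the moderator, the same Measures section lists "time since last clinic visit during which smoking was addressed, initial choice of cessation versus reduction, race/ethnicity, perceived stress" among variables measured at baseline. Elsewhere the choice appears only on the call ("After registration and brief assessment, either smoking cessation- or reduction- focused treatment will be delivered depending on patient preference") and, under Treatment Outcomes, as "the proportion of smokers who request cessation versus reduction counseling".

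**The concern.** A mediator has to change before the outcome it is meant to explain. Here the only post-baseline reading available for engagement by week 6 is taken when that window closes, typically weeks after the call that constitutes the outcome. A counseling session could itself raise confidence, autonomous motivation or attitude to NRT. More people in Choose to Change than in Usual Care are expected to have had that session. The arms can then differ on the week-6 mediator, and the mediator can correlate with engagement, even if the letter and texts changed no attitude.

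At stake is the mechanism the trial proposes: that choice-based messaging raises motivation, which in turn brings smokers into treatment. The plan as written could report that mechanism when only the counseling changed the mediator. Bootstrapping the path does not repair the time order.

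**Working it through.** **The plan's own figure.** The only stated figure tied to this outcome is Aim 1 power, 99% for 10% v 24% with 265 per arm. Pooled SE = sqrt(2 x 0.17 x 0.83 / 265) = 0.0326. Unpooled SE = sqrt((0.10 x 0.90 + 0.24 x 0.76) / 265) = 0.0321. z = (0.14 - 1.96 x 0.0326) / 0.0321 = 2.37, so power is 99.1%. It reproduces and is not in dispute. No power is stated for the exploratory aims.

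**Time order, Choose to Change, days from letter mailing.**
- First call: 12 + 2 = day 14.
- Last proactive attempt: 14 + 2 = day 16.
- Fifth text: 14 + 8 to 14 + 10 = days 22 to 24.
- First post-baseline mediator reading: 6 x 7 = day 42, which is 26 to 28 days after the attempts.

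In Usual Care a call follows within 48 hours of a clinic referral, whenever that occurs. Engagement counted by week 6 still falls at or before the week-6 reading.

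**Size if the call moves the mediator and the letter does not.** Inputs from the documents: 265 per arm and engagement of 10% and 24%. Assumed: baseline to week-6 correlation 0.5, a call effect of d SD in engagers, and a single-mediator joint test (arm to mediator and mediator to engagement both p < 0.05, adjusted for baseline).

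- Arm difference in the mediator = (0.24 - 0.10) x d = 0.14d.
- Residual variance = 1 - 0.5^2 + d^2 x (0.24 x 0.76 + 0.10 x 0.90)/2 = 0.75 + 0.1362d^2.
- SE = sqrt(variance x 2/265).
- For d = 0.5: 0.07 / 0.0769 = 0.91, which is significant with probability 14.9%. The second path compares 90.1 engagers with 439.9 others: SE = sqrt(0.75) x sqrt(1/90.1 + 1/439.9) = 0.100, z = 0.5/0.100 = 5.0, so it is almost always significant. Joint: 14.9%.
- For d = 0.25: 7.5% x 70.4% = 5.3%.
- For d = 0.8: 0.112 / 0.0795 = 1.41, giving 29.1%.

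Simulation (2,500 to 3,000 trials per cell) agrees:

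| Call effect (SD) | 0 | 0.25 | 0.5 | 0.8 |
|---|---|---|---|---|
| Engagement by week 6, full response | 0.2% | 5.5% | 15.4% | 29.1% |
| Engagement by week 6, 60% response | 0.2% | 3.5% | 9.3% | 19.2% |
| Additional calls, all randomized | 0.2% | 3.9% | 14.9% | 29.1% |
| Abstinence, all randomized | 0.2% | 1.0% | 5.4% | 20.5% |

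The 60% is the participation rate in Retention and Adherence. With no call effect the joint test is very conservative (0.05 x 0.05 = 0.25%), so that is the benchmark rather than 5%. The last two rows use the planned 7%/15% and 2%/7%, with additional calls occurring only among engagers and 1% abstinence assumed in non-engagers. The 7%/15% covers all additional calls by week 14; the documents give no rate for calls after week 6 alone.

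**Two apparent escapes.**
- *First engagement after week 6.* Those not yet engaged would number 265 - 63.6 = 201.4 and 265 - 26.5 = 238.5. At an assumed 2% to 5% that is about 4 to 10 and 5 to 12 events. The set is conditioned on a post-randomization event.
- *Engagers only.* Usual Care engagers first pass a motivation filter, because a clinic referral requires readiness to set a quit date. With a filter of 0.5 or 1 log-odds per SD, d = 0.5 and a mediator effect of 0.4 log-odds per SD (all assumed), false positives for additional calls are 10.0% and 24.8%.

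**The case against.** The strongest case is that both aims are labelled exploratory and that the magnitude rests on assumptions: the call effect, the 0.5 correlation and a single-mediator joint test, where the plan has simultaneous mediators with bootstrapping. At 0.25 SD and 60% response the rate is only 3.5%. The autonomy-support scale asks about health-care practitioners, so a Quitline call need not move it. All of this stands and limits the size. None of it changes the time order, which follows from the schedule alone.

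A second objection is that restricting mediation to later events does not remove the bias, since the rates for additional calls (14.9% and 29.1%) match those for engagement (15.4% and 29.1%). This also stands. A timing restriction gives the right order of events but needs an explicit caveat.

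A reader might infer that initial choice is a post-randomization variable recorded only in the roughly 90 of 530 participants (17%) who engage, and so cannot moderate engagement. The documents do not support that as a finding. The Measures section says the variable is measured at baseline. The Telephone Surveys section explains that enrolled participants are surveyed "Because many outcome, moderator, mediator, and control variables cannot be received from the Quitline via the EHR system for participants who do not engage". The survey description also names no instrument for discrimination, autonomous motivation or confidence, so its silence on choice proves little. The Incomplete Disclosure section, which withholds the quit-or-reduce approach from Usual Care, makes a baseline question awkward but does not exclude one. What remains is a request to confirm the item.

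**Conclusion.** The concern holds for Exploratory Aim 2, for engagement counted by week 6. The mediators are read at week -4 and then only at or after the outcome, so the planned analysis cannot separate a letter effect from a call effect. If only the call acts, false mediation is found in about 5%, 15% and 29% of trials at assumed call effects of 0.25, 0.5 and 0.8 SD with full response, and in about 3.5%, 9% and 19% at 60% response.

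Two wider inferences are not supported. The primary comparisons and their stated power do not depend on the mediators and are unaffected. Mediation of later calls and of abstinence is not ruled out by time order, because a week-6 reading can precede those events; it is open to the same contamination and can be read only as association. The initial-choice moderator is a missing detail, not a separate defect.

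**What to change.** 1. In Exploratory Aim 2 (objectives), Moderators, Mediators, and Covariates, and the Exploratory Aim 2 analysis paragraph, state that mediation of engagement by week 6 will not be tested or claimed. Report its relation to week-6 mediators as an association only.
2. For utilization and cessation, use week-6 mediators adjusted for baseline and count only outcome events after the week-6 survey: additional calls after week 6, and abstinence at the final follow-up (week 14 or 28 by timeline).
3. State that these results are associational too, because week-6 mediators may already reflect counseling received, and that the simulated bias for additional calls is about as large as for engagement.
4. Do not add first engagement after week 6 as a mediation outcome, and do not rely on an engager-only analysis.
5. Confirm that a week -4 item on cessation versus reduction exists and name it. If there is none, report choice descriptively among engagers.

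The cost is wording, with no new data. The mechanism of week-6 engagement can then not be claimed from these surveys. Additional calls completed before week 6 drop out of the utilization mediation. They may be many, since Potential Study Risks describes weekly counseling calls and outreach starts at about day 14.

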Secondary Aim 1 (Cost Evaluation): Conduct a cost-analysis to determine the cost of providing effective cessation therapy to smokers using this letter-enhanced EHR-referral and outcomes system. Evaluate the cost effectiveness of the Choose to Change letter and automated /text messages compared to usual care by calculation the cost-effectiveness ratio as the average dollars spent per successful quit.

Exploratory Aim 1 (Moderators of Intervention Effects): Evaluate motivation to quit, time since last clinic visit during which smoking was addressed, health literacy, cigarettes per day, recent smoking reduction, initial choice of cessation versus reduction, race/ethnicity, and primary language as moderators of effect of Choose to Change on treatment engagement, treatment utilization, and smoking cessation.

Exploratory Aim 2 (Mediators of Intervention Effects): Evaluate change in perceived autonomy support, autonomous motivation, confidence in ability to quit, and attitude towards NRT as mediators of intervention effects on treatment engagement, utilization, and cessation.

BACKGROUND AND RATIONALE FOR STUDY

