- 2) Seasonal Newsletters providing updates about study progress on recruitment, patient testimonies about their experiences with clinical research, NNHSC clinic updates from [name], health tips and information, and seasonal activities that support healthy lifestyles. The purpose of the newsletters is to keep participants engaged with the study in between their telephone interviews, thereby increasing retention and minimizing attrition.
- 3) Small participant incentive items using the same graphics and messaging from the general clinic campaign will be mailed with the reminder letters (e.g., water bottles, draw string bags, small ear buds, T-shirts). Consistently using the same images and themes across recruitment and retention materials will generate familiarity with the study and will serve to maintain high retention rates.

All recruitment and retention materials will be mailed from NNHSC.

Randomization and Study Conditions

Smokers identified through the SQL query from NNHSC's EHR and who consent to enroll in the NNHSC "health habits and wellness service needs study" and who complete the baseline survey will be randomized to either **Usual Care** or person-centered population management (**Choose to Change**) four weeks (week 0) after enrollment in the study (week -4). We will use a 6:6 permuted block randomization scheme to assign patients to treatment condition. Randomization will be stratified by readiness to quit, as measured using a single item question for which participants identify their level of motivation to quit smoking as measured on a 10-point scale (1 = not at all motivated; 10 =extremely motivated), race (African American versus not), and language preferred (English versus Spanish). We plan to approach 115 patients per month to enroll 40 participants per month and achieve this randomization rate (35% response rate).

Choose to Change (CtC) Intervention: Choose to Change will comprise two components: 1) a single page letter that messages choice of cessation or smoking reduction using words and a graphic; and 2) five automated text messages sent on behalf of the NNHSC providers that reinforce the central messaging of the letter.

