All outcomes of interest for **Primary Aims 1-3** are binary (treatment engagement, treatment utilization, smoking cessation) and can be analyzed using logistic regression methods. Analyses will be conducted first using an ITT principle (missing=treatment failures). We will also conduct an adherence sample analysis that includes only participants reached at the 28-week follow-up ($\geq 75\%$ of the sample based on our experience). This approach addresses the question of effectiveness more directly, but it is subject to more bias if attrition is large or differential by treatment condition. Therefore, we will complement it by analysis of non-response patterns using sociodemographic (age, gender, race, ethnicity, marital status, household income, education), and healthcare (time since last clinic visit, type of health insurance) characteristics. These can be used to create propensity scores that allow for inverse-probability-weighting (IPW) of observed outcomes^{116,117} to achieve balance across potential confounders of the treatment-to-outcome relationship. Ideally, the distribution of propensity scores will show large overlap across study conditions. If not, that will be taken as evidence that completers are not comparable on measured confounders across conditions, and that one should refrain from

PROTOCOL SHORT TITLE: Choose to Change – Reducing Tobacco Disparities

further comparisons. PROC GENMOD of SAS/STAT 9.2¹¹⁸ can handle subject-level probability weights. Similar findings across all three approaches would increase confidence in the results overall. Both raw and adjusted rates will be presented for each outcome by study condition. For the cessation outcome, we will also explore the impact of smoking history (e.g., past year quit attempts, past referral for Quitline treatment), race, and gender on non-response. We will also use propensity score modeling to examine the relationship between treatment utilization at 14 weeks and abstinence at 28 weeks. Since available data indicate little effect of NRT type on outcome, we will model NRT dose/duration, while controlling for patterns of utilization.

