Exploratory Aim 1 (Moderators of Choose to Change Effects). We will focus our search for moderators on baseline variables such as readiness to quit, health literacy,⁷¹ smoking level, time since the patient's last clinic visit in which smoking was addressed, and recent smoking reduction.⁵³ Participants who smoke more than 10 cigarettes per day, who have recently attempted to reduce their smoking, and those lower on motivational readiness to quit are expected to be disproportionately responsive to Choose to Change intervention. In addition, participants with lower literacy and those with a more recent clinic visit during which smoking was addressed are expected to be especially likely to benefit. These factors are expected to be especially responsive to the person-centered and the low-income targeted elements of the Choose to Change intervention (Figure 2), though we realize that there may be other potential moderators. Other variables to be explored as potential moderators include initial choice of smoking cessation versus reduction, and race/ethnicity. Analysis will be conducted using logistic regression, with a separate model for each outcome variable. The predictor variables will include treatment condition, the moderator variables, and their two-way interactions with condition. Sociodemographic (e.g., gender), psychosocial (e.g., perceived stress), and smoking (e.g., menthol cigarette use) variables known to influence smoking cessation will serve as covariates.

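### Randomization is stratified by readiness, race and language, but the primary logistic models name none of these factors; adding them for Aims 1 and 2 is a small, nearly free improvement

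*Combined protocol and SAP*

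**What the plan says.** The section Randomization and Study Conditions sets up permuted blocks (6:6) within strata: "Randomization will be stratified by readiness to quit, as measured using a single item question" scored 1 to 10, together with "race (African American versus not), and language preferred (English versus Spanish". It gives no cut-points for readiness.

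The Data Analysis section of the Statistical Analysis Plan says that the outcomes of Aims 1-3 "are binary (treatment engagement, treatment utilization, smoking cessation) and can be analyzed using logistic regression methods". ITT with missing counted as failure comes first. An analysis of those reached at 28 weeks follows, and then inverse-probability weighting (IPW). No terms are given for the primary models.

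The variables offered for non-response and IPW are "sociodemographic (age, gender, race, ethnicity, marital status, household income, education), and healthcare (time since last clinic visit, type of health insurance) characteristics". Race is there; readiness and language are not. Shortly afterwards the section promises: "Both raw and adjusted rates will be presented for each outcome by study condition".

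The randomization factors return only in exploratory work. The Data Analysis text on moderators expects that "those lower on motivational readiness to quit are expected to be disproportionately responsive to Choose to Change intervention", and the aims list "race/ethnicity, and primary language as moderators of effect of Choose to Change". Covariates for an outcome model are mentioned only for those moderator models, where "variables known to influence smoking cessation will serve as covariates".

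**The concern.** Stratified randomization makes the arms more alike on the stratification factors than chance alone would. If such a factor predicts outcome, a test that ignores it uses a standard error that is slightly too large. The test then tends to reject a little less often than 5% under the null and gives up some power. The three factors must be known in order to randomize, so the information is already held.

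Readiness to quit is the factor most likely to matter, and the plan treats it as important enough both to stratify on and to study as a moderator. At stake are a little power, mainly for Aim 2, and clarity about which treatment effect is reported. A logistic model with covariates estimates a conditional odds ratio, which differs from the marginal one implied by the planned rates.

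**Working it through.** **Inputs from the documents.** 265 per arm and two-sided alpha 0.05 (Power). Rates of 10% v 24%, 7% v 15% and 2% v 7% (Table 3). 66% African American (Study Sites).

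**Reproducing the stated power.** With d = p2 - p1, p = (p1 + p2)/2, s0 = sqrt[2p(1-p)/265] and s1 = sqrt[(p1(1-p1) + p2(1-p2))/265], power = Phi[(d - 1.96 s0)/s1].

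| Aim | d | s0 | s1 | z | Power | Stated |
|---|---|---|---|---|---|---|
| 1 | 0.14 | 0.0326 | 0.0321 | 2.37 | 99.1% | 99% |
| 2 | 0.08 | 0.0272 | 0.0270 | 0.99 | 83.9% | 84% |
| 3 | 0.05 | 0.0180 | 0.0179 | 0.82 | 79.5% | 80% |

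The planned powers are those of an unadjusted two-proportion comparison.

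**Effect of adjustment, by simulation.** N = 530, blocks of 12 within readiness x race x language, 40,000 trials per setting (Monte Carlo standard error about 0.2 points for power and 0.11 for type I error). Assumptions not in the documents:
- readiness uniform on 1-10 or skewed low, and linear on the logit scale;
- odds ratio (OR) of 1.2 or 1.4 per readiness point, that is 1.2^9 = 5.2-fold or 1.4^9 = 20.7-fold odds across the scale;
- 10% Spanish-preferring;
- race and language not prognostic.

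The tests are likelihood-ratio (LR) tests, so the unadjusted level differs slightly from the formula. Ranges cover the two readiness distributions. Null rates for type I error are 17% (Aim 1) and 11% (Aim 2).

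| Setting | Unadjusted | Adjusted |
|---|---|---|
| Aim 2 power, OR 1.0 | 84.9-85.0% | 84.9-85.1% |
| Aim 2 power, OR 1.2 | 85.1-85.3% | 85.8-86.0% |
| Aim 2 power, OR 1.4 | 85.8% | 87.6-88.2% |
| Aim 2 type I error, OR 1.2 | 4.8% | 5.1-5.2% |
| Aim 2 type I error, OR 1.4 | 4.3-4.6% | 5.0-5.5% |
| Aim 1 power, OR 1.4 | 99.4% | 99.6% |

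If readiness matters less under Choose to Change, as the moderator hypothesis suggests, Aim 2 power goes from 84.6-84.9% to 84.7-85.3% (OR 1.2 in Usual Care, 1.0 in Choose to Change) and from 85.1-85.3% to 85.7-86.2% (1.4 and 1.1).

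A separate run of 8,000 trials with uniform readiness held the adjusted test to the unadjusted test's actual size. The Aim 2 gain was then only about 0.3 points (OR 1.2) and 0.6 points (OR 1.4).

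**Aim 3.** Expected quits are 265 x 0.02 + 265 x 0.07 = 5.3 + 18.55, or about 24. Power for unadjusted LR, unadjusted chi-square and adjusted Firth-penalized tests is 83.3%, 82.5-82.6% and 82.1-82.3% at OR 1.2, and 82.9-83.0%, 82.0-82.1% and 82.4-82.7% at OR 1.4. Adjustment brings no net gain.

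**Odds ratio scale, Aim 2.** The marginal OR is (0.15 x 0.93)/(0.07 x 0.85) = 2.34. The conditional OR giving the same rates is 2.39 at readiness OR 1.2 and 2.50-2.55 at 1.4.

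**Sparse language group.** The documents give 10% Hispanic but no Spanish-preferring share. I take 3.4% (10% of the 34% who are not African American; 18 people) to 10% (53 people). At average event rates of 11% (Aim 2) and 4.5% (Aim 3), the chance of no event in that group is:
- Aim 2: 0.89^18 = 12% to 0.89^53 = 0.2%;
- Aim 3: 0.955^18 = 44% to 0.955^53 = 9%.

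With no event, ordinary logistic regression has no finite language coefficient.

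**The case against.** The strongest defence is that nothing is broken. The plan names no covariates, its powers are unadjusted, and the two agree, so treatment-only logistic regression is the natural reading. That stands. A reader might infer that ignoring the strata inflates type I error or undermines the stated powers. Neither follows: for Aims 1 and 2 the treatment-only test is conservative if anything, and the powers reproduce.

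A reader might also infer that the promised adjusted rates rest on no variables and leave the covariates to be picked later. That goes too far. The sentence comes straight after the weighting method and the comparison of the three approaches, so adjusted most naturally means IPW-weighted, and variables are listed for that purpose. Only an explicit label is missing. Moreover, ITT comes first and raw rates are promised, so an adjusted figure could not displace the raw comparison.

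Finally, a 2-point gain needs an OR of 1.4 per point, a roughly 21-fold range in odds for which the documents give no support, and part of that gain is test size. This also stands, and it limits the point to a modest improvement.

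**Conclusion.** The point holds as a minor one. The primary models for Aims 1-3 name none of the three randomization factors, although using them costs almost nothing. The treatment-only analysis is valid and consistent with the power section. For Aim 2, adjustment is worth under about 1 point of power at a readiness OR of 1.2 and up to about 2 points at 1.4, less once test size is equalized. For Aim 1 it is negligible because power is already 99%. For Aim 3 there is no net gain, so the case does not extend to adjusting that aim.

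These sizes rest on assumed readiness effects and distributions, and on race and language not being prognostic. The absence of the factors from the primary models rests on the text alone.

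**What to change.** Add one paragraph to the Data Analysis section:

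- **Aims 1 and 2.** The primary ITT logistic model contains arm, readiness (the 1-10 score, or as coded for randomization), race (African American or not) and language (English or Spanish). Report standardized rates by arm and the risk difference. Keep the unadjusted comparison as a sensitivity analysis.
- **Sparse language group.** If no events occur among Spanish-preferring participants, drop the language term or use Firth-penalized likelihood. State in advance which.
- **Aim 3.** Keep the unadjusted test as primary. It matches the power calculation and suits about 24 expected quits.
- **Labels.** Report IPW rates under their own name, separate from the model-standardized rates.

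No extra patients or data are needed. There are two downsides. The adjusted odds ratio is conditional (about 2.39 to 2.55 against 2.34 marginal for Aim 2), so the reported quantity must be named. The adjusted LR test can also run slightly above 5% (about 5.5% in simulation).
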